4.6.5.2 Presentations

Treatment emergent abnormalities

The number of subjects with treatment emergent ANCA positivity will be presented in a shift table with the categories positive and negative, by treatment group.

4.6.6 Vital Signs

4.6.6.1 Definitions and Derivations

Vital signs (supine blood pressure (BP), pulse rate and body temperature) will be performed at timepoints according to the schedule of activities in Section 1.3 of the CSP.

For baseline vital signs assessments, the following order of eCRF forms should be used.

- VS4 (if not missing),
- VS3 (if VS4 is missing),
- VS5 (if both VS4 and VS3 are missing),

If all above are missing, earlier assessments should be used.

Observations from VS7 will not be considered as baseline since this is completed post first dose of IP as per the eCRF instructions.

The same logic applies to all post-randomisation visits.

Vital signs shift from baseline will be defined based on the following categorisation:

- Systolic BP: High if ≥ 140 ; Normal if < 140 and ≥ 90 ; Low if < 90
- Diastolic BP: High if ≥ 90 ; Normal if < 90 and ≥ 60 ; Low if < 60
- Pulse rate: High if ≥ 100 ; Normal if < 100 and ≥ 50 ; Low if < 50 .

Treatment emergent abnormalities

Vital sign treatment emergent abnormalities are determined as follows:

- Systolic BP (mmHg):
 - Observed value \geq 140 and absolute increase of \geq 20 from baseline for high level.
 - Observed value $<$ 90 and absolute decrease of \geq 20 from baseline for low level.
- Diastolic BP (mmHg):
 - Observed value \geq 90 and absolute increase of \geq 10 from baseline for high level.
 - Observed value $<$ 60 and absolute decrease of \geq 10 from baseline for low level.
- Pulse rate (beats/min):
 - Observed value \geq 100 and absolute increase of \geq 20 from baseline for high level.
 - Observed value $<$ 50 and absolute decrease of \geq 20 from baseline for low level.

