Timeframe for start of medication to be considered a concomitant medication is extended to match on-treatment period.	03/08/2024	
Timeframe for start of medication to be considered a concomitant medication is extended.
 
Rescue medications removed from presentation as part of concomitant medications.
		
Correction to match definition of on-treatment period.
 
Correction, there is no rescue medication definition in the study.

Endpoint analyses	03/08/2024	
Rescue medications removed as a potential intercurrent event in the estimand description since we do not have a rescue medication definition in the study.
 
Updated wording in regarding concomitant medication in definition of estimands for primary and supplementary estimands.
		
Correction, there is no rescue medication definition in the study.
 
Alignment with Safety estimand wording.

Statistical analysis for primary endpoints	03/08/2024	Updated threshold for HbA1C subgroup categories. Subgroup analysis: Denominator for 5 % (when separate models will be fitted for each subgroup category) changed from randomised subjects to FAS.		Correction of typo Correction
Statistical analysis for secondary endpoints	03/08/2024	IL-6 observations reported as LLoQ will be imputed as described in Section 3.3.1.3. Description of IL-6 categories for first supplementary analysis (logistic regression) updated. Update of second supplementary analysis (ANCOVA) to include all subjects with a matched pair of lab analysis method for IL-6. Method added as covariate in the model.		Clarification Correction of typo Correction

		CCI [REDACTED] [REDACTED] [REDACTED] [REDACTED] [REDACTED]		CCI [REDACTED] [REDACTED]
Safety analysis	03/08/2024	
Data from the post-dose vital signs eCRF form VS7 will not be considered as baseline.
 
The order for selecting data from eCRF forms for baseline vital signs will also be applied for post-randomisation visit.
 
Overdose listing added.
		
Clarification
 
Clarification
 
Correction

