3.3.2 Visit Window

Visit windows will be used for analysing visit-based data and are based on the target day for a scheduled visit, see Schedule of Activities in the CSP. The range of the windows for scheduled on-site assessments are shown in

Table 1.

The visit closest to the target day and within the visit window is assigned. This can be a scheduled or unscheduled assessment.

Table 1 Visit windows for on-site assessments

Scheduled assessment	Visit	Target Day	Visit window (days)
All endpoints			

Week 4	4	29	[2 ¹ , 57]
Week 12	6	85	[58, 99]
Week 16	8	113	[100, 141]
Week 24	9	169	[142, 211]
Week 36	10	253	[212, 294]
Week 48	11	336	[295, 350]
Week 52	12	365	>350

¹. The Week 4 visit window also includes post-dose vital signs assessments (VS7) taken on the day of randomisation, but after the baseline assessment.

The analysis visit window as defined in Table 1 will not be used for the Orthostatic blood pressure test at 12 weeks. Instead, the nominal visit number will be used for this assessment.

Analysis visit windows for **CCI** will be described in Sections 4.2.9.4 and 4.2.18.1. Baseline is defined in Section 3.3.1.1.

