4.6.6.2 Presentations

Values and absolute change from baseline will be presented based on SAS by visit for continuous variables using descriptive statistics for all scheduled assessments after baseline, by treatment group.

Vital sign shift from baseline to maximum/minimum on-treatment/on-study value will be presented.

Treatment emergent abnormalities

The number and percentage of subjects with vital signs treatment emergent abnormalities will be presented by treatment group.

Key subject information

Key subject information will be presented for subjects with treatment emergent abnormalities as defined in Section 4.6.6.1.

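### SAP 4.6.6.1 can be read as allowing earlier vital-sign values to fill empty follow-up visits, and Table 1 footnote 1 lets a Day 1 post-dose reading stand as Week 4

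*SAP*

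**What the plan says.** SAP 4.6.6.1 opens its vital-sign rule with "For baseline vital signs assessments, the following order of eCRF forms should be used" and lists VS4, then VS3, then VS5. The rule goes on: "If all above are missing, earlier assessments should be used". A further sentence removes one form from baseline: "Observations from VS7 will not be considered as baseline since this is completed post first dose of IP as per the eCRF instructions". Directly after that comes "The same logic applies to all post-randomisation visits".

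SAP 3.3.2 governs which reading belongs to which visit: "The visit closest to the target day and within the visit window is assigned". Footnote 1 to its Table 1 makes an addition for vital signs: "The Week 4 visit window also includes post-dose vital signs assessments (VS7) taken on the day of randomisation, but after the baseline assessment".

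SAP 3.3.3 settles ties on opposite sides of the target day in favour of the earlier assessment. It also ranks the sources when one visit has several vital-sign measurements: the vital-signs reading first, then the supine pressure before the orthostatic test, then the one before the walk test. It has no step back to an earlier visit.

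SAP 4.6.6.2 states the output: "Values and absolute change from baseline will be presented based on SAS by visit for continuous variables". The SAP amendment history for version 4 describes the change to the form rule as "The order for selecting data from eCRF forms for baseline vital signs will also be applied for post-randomisation visit".

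**The concern.** Falling back to an earlier reading is sound for baseline, where the last value before treatment is what is wanted. At a follow-up visit the same step is last observation carried forward. A participant with no Week 24 or Week 48 vital signs would receive an older value, possibly one from before treatment. The by-visit n would look complete, and late means would be pulled toward early ones. SAP 3.3.1.3 rules out imputing missing safety laboratory data, but there is no matching general sentence for vital signs to close off this reading.

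The VS7 footnote is a separate problem, and its wording is not in doubt. A reading taken on the day of the first dose can be summarised as a Week 4 value, so its change from baseline is a same-day change.

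Blood pressure and pulse rate, as observed values and as change from baseline, are named Part A safety assessments (Protocol Table 4; SAP Table 4). Two programmers working from this text could produce different by-visit tables.

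**Working it through.** The plan gives no figure to reproduce here. The check sets the rules side by side and applies the window arithmetic.

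**1. What the same-logic sentence could cover.** Three elements precede it.

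- *Form order (VS4, VS3, VS5).* This fits 3.3.3, which also ranks sources within a visit, and it is what the version 4 entry describes.
- *Fallback to earlier assessments.* This conflicts with 3.3.2 and 3.3.3 (step 2).
- *Exclusion of VS7.* This conflicts with Table 1 footnote 1, which admits VS7 to Week 4.

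Even on the form-order reading, VS7 has no place in the VS4/VS3/VS5 list that would govern Week 4.

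**2. Fallback against the windows.** Inputs are the target days and windows in SAP Table 1.

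| Visit being filled | Window (days) | Previous scheduled target day | Inside window? |
|---|---|---|---|
| Week 12 | 58–99 | 29 | No |
| Week 16 | 100–141 | 85 | No |
| Week 24 | 142–211 | 113 | No |
| Week 36 | 212–294 | 169 | No |
| Week 48 | 295–350 | 253 | No |

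The windows do not overlap. An earlier reading inside the window is already eligible under 3.3.2, so for it the fallback adds nothing. An earlier reading outside the window may not be assigned under 3.3.2, so using it breaks that rule.

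**3. When VS7 becomes the Week 4 value.** The Week 4 target is Day 29 and the window is Days 2–57, plus VS7 on Day 1. Distance from target = |day − 29|.

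- VS7 on Day 1: |1 − 29| = 28 days.
- Any reading on Days 2–56: at most 27 days (|2 − 29| = 27; |56 − 29| = 27). It is closer and displaces VS7.
- A visit held within the protocol's ±3 days (Days 26–32): at most 3 days.
- A lone reading on Day 57: |57 − 29| = 28 days. This ties with Day 1 on the opposite side of the target, and 3.3.3 selects the earlier assessment, so VS7 is used.

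VS7 is therefore reported as Week 4 exactly when a participant who has a VS7 reading has no other reading on Days 2–56, even if a real reading exists on Day 57.

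**4. Which outputs can move.** By-visit values, changes from baseline and n can move. Maximum/minimum shifts and abnormality counts do not: a post-baseline value that has already been observed adds nothing when repeated, and a repeated baseline value shows no change from baseline.

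**The case against.** The strongest reply is that the SAP already blocks carry-forward. Section 3.3.2 assigns only in-window readings, 3.3.3 gives a within-visit ranking that is the natural meaning of the sentence, and the version 4 entry says that only the order was extended. The on-treatment analysis is also implemented by censoring data 14 days after premature discontinuation (SAP 4.6), which carrying values into later visits would contradict. This stands as evidence of intent, and it is why the conclusion is that carried values could enter the tables. It does not repair the current sentence, which follows the fallback step without limiting itself to form order.

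On VS7, the footnote is a deliberate version 4 clarification, and VS7 is used only as a last resort. The reason given for excluding VS7 from baseline, that it is recorded after the first dose, has no force after randomisation, so the clash with 4.6.6.1 arises only if the sentence is read to include that exclusion. Both points are fair. They limit how often a Day 1 reading is labelled Week 4, but they do not make the label right.

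A reader might infer more than the documents support:

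- *That the plan prescribes carry-forward.* The other rules point the other way.
- *That about 9% of late values are affected.* Protocol 9.2 expects 600 of 660 participants to have complete safety data, and 60/660 = 9.1%. That is not a vital-sign missing rate at any visit, and it is not given by arm.
- *That rash-related stopping would bias the arms apart.* Protocol 7.1 keeps participants who stop study drug in scheduled visits, and neither document gives missing-visit rates by arm.
- *That VS7 matters only for participants randomised before 12 August 2022.* SAP 4.6.8.1 gives that date for stopping the post-dose orthostatic assessment. The SAP does not say that VS7 is the form for it.

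**Conclusion.** The point holds in two limited parts. First, the same-logic sentence is ambiguous. Its literal reading would let earlier values fill empty follow-up visits, against SAP 3.3.2 and 3.3.3. Second, footnote 1 does place a Day 1 post-dose reading in the Week 4 summary for any participant with a VS7 reading and none on Days 2–56, including one whose only other reading in the window is on Day 57.

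The size cannot be computed, because the documents give neither a missing-visit rate for vital signs nor a difference between carried and true values. Exposure is confined to descriptive by-visit means, changes and n. Protocol 9.4.3 makes the safety analyses descriptive with no p-values, so no efficacy test, error rate or power figure is touched. The change is still worth making, because the text permits wrong by-visit safety values and costs almost nothing to correct.

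**What to change.** In SAP 4.6.6.1, replace the same-logic sentence. State that the VS4, VS3, VS5 order applies within the analysis window of each post-randomisation visit, and that a visit with no in-window reading is left missing with no earlier value used.

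In SAP 3.3.2, remove footnote 1 from Table 1 and report VS7 as a separate Day 1 post-dose timepoint. Say that VS7 still counts toward on-treatment and on-study maximum and minimum values and toward treatment-emergent abnormalities. This also settles the possible clash between the footnote and 4.6.6.1.

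The cost is about two sentences of SAP text, one extra timepoint in the vital-sign table and a slightly smaller by-visit n.

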4.6.6.2 Presentations

Values and absolute change from baseline will be presented based on SAS by visit for continuous variables using descriptive statistics for all scheduled assessments after baseline, by treatment group.

Vital sign shift from baseline to maximum/minimum on-treatment/on-study value will be presented.

Treatment emergent abnormalities

The number and percentage of subjects with vital signs treatment emergent abnormalities will be presented by treatment group.

Key subject information

Key subject information will be presented for subjects with treatment emergent abnormalities as defined in Section 4.6.6.1.

4.6.7 Electrocardiogram

4.6.7.1 Definitions and Derivations

Single 12-lead ECG (standard ECG with a paper speed of 25-50 mm/second covering at least 6 sequential beats) will be obtained according to the schedule of activities in Section 1.3 of the CSP.

Treatment emergent abnormalities

ECG treatment emergent abnormalities are defined as subjects with abnormal clinically significant results that were not present at baseline.

4.6.7.2 Presentations

Summary statistics will be shown for the following categories for SAS by treatment group:

- Heart rhythm category
- Overall ECG evaluation
- Was the ECG clinically significant?

Shifts from baseline to last observation in ECG overall evaluation will be analysed in terms of normality and clinical significance.

Treatment emergent abnormalities

The number and percentage of subjects with ECG treatment emergent abnormalities will be presented by treatment group for SAS, where the percentage is based on number of subjects per treatment group with a baseline value and at least one post-baseline value.

Key subject information

Key subject information will be presented for subjects with treatment emergent abnormalities.

Listings

A listing for all subjects will present date of ECG performance, categories listed above and reasons if conduction was abnormal.

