6.3 Measures to Minimise Bias: Randomisation and Blinding

All participants will be centrally assigned to randomised study intervention using an IRT/RTSM. This computerised randomisation procedure will ascertain allocation concealment and will assign the participants 1:1:1 to two dose levels of AZD4831 or matching placebo in Part A and 1:1 to AZD4831 or matching placebo in Part B. For Part A, in the event that randomisation to the AZD4831 5 mg treatment arm is stopped during the study due to safety in either the whole study or in specific countries or ethnic populations, the remaining participants in that cohort will be randomised at a 2:1 ratio to 2.5 mg AZD4831 or matching placebo.

The randomised study population will be capped by neutrophil count, 6MWD and KCCQ-TSS in both Part A and Part B. The capping will consist of:

- The proportion of participants having neutrophil count $> 4 \times 10^6/\text{mL}$ at Screening will be 60%-80%
- A maximum of 25% of the participants can have 6MWD ≥ 350 and ≤ 400 meters at randomisation visit.
- A maximum of 30% of the participants can have KCCQ-TSS > 80 and ≤ 90 at randomisation visit.

LVEF value at screening and atrial fibrillation/flutter status on ECG at Screening (Visit 1) may also be capped in the IRT/RTSM to avoid over- or under-representation of these participant subgroups.

The randomisation will be stratified by neutrophil count in both Part A and Part B.

The study will be blinded to both participants and Investigators/site staff as well as to the sponsor (designated sponsor personnel will be unblinded as part of DRC and URC in Part A as described in Appendix A 5). The IRT/RTSM will provide to the Investigator(s) the kit identification number to be allocated to the participant at the dispensation visit. Study intervention will be dispensed at the study visits summarised in the SoA (See Section 1.3). Routines for this will be described in the IRT/RTSM user manual that will be provided to each centre.

The randomisation code should not be broken except in medical emergencies when the appropriate management of the participant requires knowledge of the treatment randomisation. The investigator documents and reports the action to AZ, without revealing the treatment given to participant to the AZ staff.

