For Part B, the following AEs are considered treatment emergent: AEs with an onset date on or after baseline or a worsening of pre-existing AEs on or after baseline. A treatment emergent abnormality is defined as a switch in a safety parameter from not-abnormal at baseline to abnormal at post-baseline assessments accordingly to predefined criteria specified in the SAP.

Vital signs

Vital sign parameters will be presented for each treatment group. Summary statistics for continuous variables cover n, mean, SD, Min, Q1, median, Q3, and Max. For each scheduled post-baseline visit, descriptive statistics for all vital sign parameters will be presented for observed values and change from baseline. Details of vital sign analyses will be provided in the SAP.

In Part B, time to first treatment emergent abnormality will also be presented.

Laboratory

Laboratory parameters will be presented for each treatment group. Summary statistics for continuous variables cover n, mean, SD, Min, Q1, median, Q3, and Max. For each scheduled post-baseline visit, descriptive statistics for all clinical chemistry and haematology parameters will be presented for observed values and change from baseline. A frequency table presents number of subjects reporting at least one treatment emergent change in selected laboratory parameters. Details of laboratory analyses will be provided in the SAP.

In Part B, time to first treatment emergent abnormality will also be presented.

Electrocardiogram

Electrocardiogram evaluation will be summarised and presented by treatment group for baseline and for each scheduled post-baseline assessment. More details of ECG analyses will be provided in the SAP.

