4.6.8 Other Safety Assessments

4.6.8.1 Definitions and Derivations

Orthostatic blood pressure test

Orthostatic hypotension related measures are derived from the orthostatic BP measurements. The orthostatic hypotension test is described in section 8.2.2 in the CSP. It was communicated to sites on 12 August 2022 to stop performing the post-dose assessment at the day of randomisation.

Therefore, only subjects randomised prior to 12 August 2022 will be at risk in the analysis presenting results for the post-dose test at the day of randomisation. All observations will be presented in the listing regardless of when the test was performed.

The following definitions will be applied:

- BP decrease: a decrease ≥ 20 mmHg in systolic blood pressure or ≥ 10 mmHg in diastolic blood pressure.
- BP decrease reported as AE: a BP decrease and a reported AE of Orthostatic Hypotension the same day post-first dose or within the same day of the 12 weeks measurement.
- Symptomatic BP decrease: BP decrease which the investigator judge that there were symptoms that were related to the orthostatic blood pressure measurement.
- Asymptomatic BP decrease: BP decrease which the investigator judge that there were no symptoms that were related to the orthostatic blood pressure measurement.

These categories will be presented at three timepoints

- post-first dose irrespective of baseline status,
- only post-first dose (including only subjects with no observed BP decrease pre-first dose), and
- at 12 weeks.

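### The ECG treatment-emergent percentage has no at-risk denominator, so if the event is judged on the overall clinical-significance flag its absolute size is diluted; the ECG shift table also uses only the last ECG

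*SAP*

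**What the plan says.** SAP 4.6.7.1 (Electrocardiogram) defines the event: "ECG treatment emergent abnormalities are defined as subjects with abnormal clinically significant results that were not present at baseline". It does not say whether presence at baseline is judged on the overall rating of the tracing or abnormality by abnormality.

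SAP 4.6.7.2 gives the denominator, "where the percentage is based on number of subjects per treatment group with a baseline value and at least one post-baseline value", and lists three summarised items: heart rhythm category, overall ECG evaluation, and a single question per tracing, "Was the ECG clinically significant". It then adds: "Shifts from baseline to last observation in ECG overall evaluation will be analysed in terms of normality and clinical significance". Participants with a treatment-emergent abnormality also get key subject information, and a listing covers every participant.

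Other safety domains are handled differently:

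- Vital signs (SAP 4.6.6.2): "Vital sign shift from baseline to maximum/minimum on-treatment/on-study value will be presented". Urinalysis (SAP 4.6.4.2) likewise shifts to the maximum and minimum assessment in each period.
- Orthostatic blood pressure (SAP 4.6.8.1) is shown irrespective of baseline status and also as "only post-first dose (including only subjects with no observed BP decrease pre-first dose").
- For Part B only, Protocol 9.4.3 states: "A treatment emergent abnormality is defined as a switch in a safety parameter from not-abnormal at baseline to abnormal at post-baseline assessments".

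**The concern.** A percentage labelled treatment-emergent is normally read as the risk of a new abnormality among people who could develop one. In the ECG table the numerator looks at baseline status and the denominator does not. If some participants cannot have the event by definition, the percentage is lower than the risk it appears to describe, by an amount the table does not show.

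Some participants could well be flagged at baseline. The trial enrols people with atrial fibrillation or flutter, who have their own NT-proBNP entry limits (Protocol 5.1.1), and Protocol 6.3 says "atrial fibrillation/flutter status on ECG at Screening (Visit 1) may also be capped".

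The shift table does use baseline status, but it compares baseline only with the last ECG. A participant who goes from normal to abnormal and back is shown there as unchanged. If the abnormality was not rated clinically significant, the treatment-emergent table does not capture that participant either.

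**Working it through.** The documents state no ECG rate, so there is no planned figure to reproduce.

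**Step 1: which reading of the definition.**

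- *By flag:* the event is a clinically significant ECG after a baseline ECG that was not clinically significant. Participants flagged at baseline cannot count.
- *By finding:* a participant with one clinically significant abnormality at baseline can still count for a different new one. Such participants remain at risk, and the full denominator is not wrong on this ground.

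The flag reading fits the collected items better. The Part A ECG endpoint is the investigator's evaluation (Protocol Table 4), significance is one question per tracing, and the SAP has no rule for comparing individual findings between visits. For laboratory values, by contrast, SAP 4.6.3.1 has a rule that lets a participant abnormal at baseline count if a later value is more extreme. The ECG section has none. The text still does not exclude the finding reading.

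**Step 2: size on the flag reading.**

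Inputs:

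- b = share of evaluable participants flagged at baseline. Not in the documents; assumed 0% to 40%.
- r = risk among those not flagged. Not in the documents; assumed 5% in one arm and 8% in the other.
- 200 evaluable participants per arm, for illustration (the per-arm number in Protocol 9.2).

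Formula: reported percentage = r × (1 − b), so the relative understatement is b.

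In counts at b = 10%, 180 of 200 are at risk. Events are 0.05 × 180 = 9 and 0.08 × 180 = 14.4. Divided by 200 these give 4.5% and 7.2%; divided by 180 they give 5% and 8%.

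| b | Reported percentages | Difference (points) | Ratio |
|---|---|---|---|
| 0% | 5.0 vs 8.0 | 3.0 | 1.6 |
| 2% | 4.9 vs 7.84 | 2.94 | 1.6 |
| 10% | 4.5 vs 7.2 | 2.7 | 1.6 |
| 20% | 4.0 vs 6.4 | 2.4 | 1.6 |
| 40% | 3.0 vs 4.8 | 1.8 | 1.6 |

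The factor (1 − b) cancels in the ratio when b is equal in the arms, which randomisation gives on average. Chance imbalance can move it. At b = 30% with 200 per arm, the standard deviation of the difference in b is √(0.3 × 0.7 × 2/200) = 0.046, so 95% limits are about ±9.0 points. At those limits the ratio is multiplied by between (0.70 − 0.045)/(0.70 + 0.045) = 0.88 and its inverse, 1.14.

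**Step 3: the shift table.** Take ECGs rated normal at baseline, abnormal but not clinically significant at a middle visit, and normal at the last visit.

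- Shift to last: normal to normal.
- Treatment-emergent table: no event.
- By-visit summary (Protocol 9.4.3): one abnormal ECG in that visit's count, not linked to the participant's baseline.
- Listing: present.

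A shift to the worst evaluation would show normal to abnormal.

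**The case against.** The strongest reply is that the definition can be read by finding, in which case participants abnormal at baseline belong in the denominator. That stands as a possibility, and it is a reason to settle the wording. Nor do the documents give b or say that atrial fibrillation or flutter is rated clinically significant. Enrolling such participants shows how b could be above zero, not that it is large. The denominator is also disclosed, and as an incidence among all evaluable participants the percentage is valid; adverse-event percentages likewise use the whole safety set (SAP 4.6.2.2).

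A reader might infer several stronger things that the documents do not support:

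- *That participants abnormal at baseline are never assessed.* They are in the rhythm and evaluation summaries, the shift table and the listing. Clinically relevant deterioration in protocol-mandated measurements is also reportable as an adverse event (Protocol 8.3.5).
- *That transient changes appear in no table.* By-visit summaries and the listing contain them. A clinically significant one absent at baseline also counts as treatment-emergent, since that definition is not tied to the last ECG.
- *That the shift table mainly reflects off-drug ECGs in those who stop early.* SAP 4.6 requires ECG tabulations for both periods, and On-treatment ends no later than 14 days after the last dose (SAP 3.3.1.5). Off-drug data in the On-study period are the declared treatment-policy approach.
- *That the comparison between arms is distorted.* With b similar across arms, the ratio is not.

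**Conclusion.** The point holds in limited form. On the flag reading, the better fit to the items collected, the absolute ECG percentage and the risk difference are multiplied by (1 − b). At b = 10% the assumed 3.0-point difference is shown as 2.7 points; at b = 0, or on the finding reading, there is no dilution. The size rests wholly on assumed values of b and r. The shift to the last ECG leaves resolved changes without a within-participant display, although the data are reported in other forms. Safety analyses are descriptive, without p-values (Protocol 9.4.3), so alpha, power and the efficacy conclusions are untouched. The change is still worth making: it costs little, and the SAP already uses a baseline-restricted presentation for orthostatic blood pressure.

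**What to change.** In SAP 4.6.7:

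1. State that the event is judged on the overall clinical-significance flag.
2. Base the percentage on participants whose baseline ECG was not clinically significantly abnormal and who have at least one post-baseline ECG in the analysis period, or show both denominators.
3. Present the shift from baseline to the worst post-baseline evaluation in each of the On-treatment and On-study periods, in addition to or instead of the shift to the last ECG. This parallels the maximum/minimum shifts for vital signs and urinalysis.

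All of this uses items already collected. The cost is SAP wording and minor programming, and the reported percentages will be somewhat higher if any participants are flagged at baseline.
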